11.2. Quality assurance

11.2.1. Data collection

The data will be collected on an electronic case report form and directly input via the Internet. Only the investigators and the Investigator's Clinical Research Assistants (CRAs) appointed by the later and duly authorized by the sponsor will be authorized to enter the data.

Data will be handled by an online trial management software on the Internet (Macro v4, Infermed Company); it will be transferred and monitored remotely in real time.

The study CRA and/or any other person appointed by the sponsor will be available to assist the investigators in carrying out the study and to ensure that the trial is carried out in accordance with the protocol.

The study CRA will contact the investigators regarding the study implementation visit.

All of the necessary data will be collected on an electronic case report form provided by the sponsor. The generic names of the concomitant medication will be given in French.

Corrections made to the original data must be justified. These corrections will be automatically dated and signed by the authorized member of staff via the personalized password allocated at the start of the study.

The case report form will be validated by the investigator or the CRA at the authorized center whenever data is entered.

Laboratory data exceeding normal limit values will be commented upon if they are considered clinically significant. Data other than that requested within the scope of the protocol can be collected as additional data; their interest will be specified.

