7.3. Safety

Patients will be evaluable for safety if they have received at least one treatment administration. Safety will be evaluated using clinical examinations, which will comprise vital signs analysis, clinical assessment of AEs, changes in laboratory parameters (hematological and biochemical, including liver function tests) and any other analyses that may be considered necessary. Safety profile will be continuously followed during treatment up to 30 days after the last treatment administration or until the start of a new antitumor therapy, whichever occurs first. All AEs will be classified according to the NCI-CTCAE, v4.03.

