8. STUDY ENDPOINTS

8.1. Primary endpoint

Phase I / Dose escalation part

Primary objective of the phase I trial is to establish the recommended phase II dose (RP2D), the maximum tolerated dose (MTD) evaluated on the first cycle (D1 to D21), the safety profile, and the Dose Limiting Toxicities (DLT) of trabectedin given in combination with durvalumab.

Definition:

Dose-limiting toxicity (DLT):

A DLT is defined as an AE or laboratory abnormality that fulfills all the criteria below:

- Begins on the first 21 days of treatment.
- Is considered to be at least possibly related to the study treatment.
- Meets one of the criteria below, graded as outlined or according to NCI-CTCAEv4.03 :
 - Any grade-4 toxicity (except for vomiting without maximal symptomatic/prophylactic treatment and if toxicity is transaminitis, but which have to be resolved at Day 21, i.e. return to Baseline or grade 1).
 - Grade-3 non-haematological toxicity lasting > 7days (except for 1rst episode of nausea without maximal symptomatic/ prophylactic treatment and if toxicity is transaminitis, which have to be resolved at Day 21, i.e. return to Baseline or grade 1).
 - Grade-3 hematologic toxicity lasting for > 7days.
 - Grade 4 neutropenia with fever.
 - Grade > 2 thrombocytopenia with bleeding.

Endpoints:

- Toxicity graded using the common toxicity criteria from the NCI-CTCAE v4.03.
- Incidence rate of DLT at each dose level during the first 21 days.

Phase I / Expansion cohorts

Primary objective of the expansion cohorts is to evaluate preliminary signs of the antitumor activity of trabectedin given in combination with durvalumab in terms of objective response under treatment. Following RECIST v1.1 recommendations ([appendix 3](#)):

- Objective response rate (ORR) is defined as the proportion of patients with complete or partial response (CR, PR) as per RECIST v1.1 criteria.
- Objective response under treatment is recorded from study treatment initiation until the end of treatment and determined once all the data for the patient is known.
- Claimed responses will have to be confirmed at least 4 weeks later to ensure responses identified are not the result of measurement errors.
- **Disease status under treatment, whatever the response observed, will be centrally reviewed for all patients, by an independent expert radiologist. Reviewed data will be used for the efficacy analysis.**

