10.2. Definition

10.2.1. *Adverse event*

An adverse event is defined as any untoward medical occurrence which occurs in a patient, a clinical investigation subject. Adverse events include, but are not limited to:

- Abnormal test findings,
- Clinical symptoms and signs,
- Changes in physical examination findings,
- Hypersensitivity,
- Drug abuse,
- Drug dependency,
- Any suspected transmission of an infectious agent via a medicinal product.

As well as signs and symptoms resulting from:

- Drug overdose,
- Drug withdrawal,
- Drug misuse,
- Drug interactions,
- Extravasation,
- Exposure during pregnancy,
- Exposure during breastfeeding,
- Medication error,
- Occupational exposure.

10.2.2. *Serious adverse event*

A Serious Adverse Event (SAE) is defined as an adverse event regardless of the dose and that:

- results in death (fatal) and/or,
- is life-threatening and/or,
- requires inpatient hospitalization or prolongation of existing hospitalization and/or,
- results in persistent or significant disability/incapacity and/or,
- results in congenital anomaly/birth defect and/or,
- is medically significant.

Medical and scientific judgment is exercised in determining whether an event is an important medical event. An important medical event may not be immediately life-threatening and/or result in death or hospitalization. However, if it is determined that the event may jeopardize the patient or may require intervention to prevent one of the other outcomes listed in the definition above, the important medical event should be reported as serious. Examples of such events are intensive treatment in an emergency room or at home for allergic bronchospasm, blood dyscrasias or convulsions that do not result in hospitalization, or development of drug dependency or drug abuse.

Any suspected transmission via a medicinal product of an infectious agent, pathogenic or non-pathogenic, is assessed as a serious adverse event with the seriousness criterion important medical event. The event may be suspected from clinical symptoms or laboratory findings indicating an infection in a patient exposed to a medicinal product. The terms "suspected transmission" and "transmission" are considered synonymous.

Any abnormal laboratory's result resulting as a grade 4 in the CTCAE v4.03 will be considered a serious adverse event even if this event is not clinically relevant.

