3.2.3 Primary endpoint

- Dose escalation part

Criteria	eFORM Variables	Control / program (TOL=1)
Toxicity will be graded using the common toxicity criteria from the NCI v4.0.	ADVERSE EVENT FORM AEVENT (adverse event) AESAE (is a serious adverse event) AE_NUMAE (Toxicity number) DT_SAE , DT_AE (date of beginning) DTENDAE (date of the end or death) INIT_INT, MAX_INT (intensity) TRAB_REL (relation to Trabectedin) DURV_REL (relation to Durvalumab) AE_TRA_MOD (Trabectedin modification) AE_DUR_MOD (Durvalumab modification) AE_OUTC (outcome)	Listing of Adverse events + descriptive statistics
Incidence rate of DLT will be reported at each dose level on cycle 1.	CYCLE 1 – TREATMENT DOSE_TRA DOSE-LIMITING TOXICITY FORM DT_EVENT OCC_CYC (occurred for the first 21 days) GR4_TOX GR3_NHT GR3_HT GR3_NEU GR2_THR OTH_DLT	Listing Of DLT + rate of DLT (Number of DLT / TOL) descriptive statistics

- Expansion cohorts

Criteria	eFORM Variables	Control (TOL=1)
Objective response rate, defined as the rate of complete or partial response according to RECIST v1.1	ASSE_CYC (TUMOR ASSESSMENT) DT_MEASC (date of measurement) ME1RTLC-ME5 RTLC (measures of lesions) SUM_RTLC (largest diameters) EVA1RLNMC-EVA5 RLNMC (non-measurable lesions eval) RES_RTLC, RES_RNTLC (target and non-target lesions) OV_REV (overall response) CR=1, PR=2, SD=3, PD=4, NE=5 New variables : NB_BORR (nb of objective response case) END OF STUDY (END_STU) DT_EOS (date of end of study)	Status at each TUMOR ASSESSMENT

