4.3.11 Safety: Adverse events (AE)

Table 11.1. For all patients assessable for efficacy: Number and percentage of AE observed by SOC and type of event

Table 11.2. For each patient assessable for safety: Event number, adverse event, serious adverse event (Y/N), SOC, date of event, initial intensity, maximum intensity, treatment modification, imputability, outcome, date of the end or death

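### Graded toxicity is analysed only from AE-form entries: no SAP output uses the on-treatment laboratory values, and no rule says how grade 1-3 values become AE records

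*Protocol*

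**What the plan says.** Protocol 8.1 gives the escalation part two primary endpoints: "Toxicity graded using the common toxicity criteria from the NCI-CTCAE v4.03", and the incidence of DLT at each dose level. Toxicity in the expansion cohorts is a secondary endpoint (8.2), but section 3.2 bases the RP2D on safety data from both parts, together with PD data.

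SAP 3.2.3 states "Toxicity will be graded using the common toxicity criteria from the NCI v4.0". Every source variable it names for this is on the adverse event form, and the output is "Listing of Adverse events + descriptive statistics". The DLT endpoint is drawn from a different source, the "DOSE-LIMITING TOXICITY FORM". The summary safety table in SAP 4.3.11 is "Number and percentage of AE observed by SOC and type of event".

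On laboratory data, Protocol 7.3 includes in the safety evaluation "changes in laboratory parameters (hematological and biochemical, including liver function tests". Section 4.7 sets the sampling days. Section 10.2.1 lists abnormal test findings among adverse events without a significance condition. Section 10.2.2 adds that a grade 4 laboratory result "will be considered a serious adverse event even if this event is not clinically relevant". Section 11.2.1 says: "Laboratory data exceeding normal limit values will be commented upon if they are considered clinically significant".

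**The concern.** The protocol promises a laboratory-based safety evaluation and collects the data for it, but the SAP has no step that turns those data into a result. A laboratory toxicity enters the graded-toxicity analysis only if someone has written it on the AE form. At grade 4 an explicit rule forces the entry. Below grade 4 there is a general definition, no entry instruction, and a nearby sentence that brings in a judgement of clinical significance.

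This matters because laboratory events make up much of the expected toxicity. Protocol 1.3.3 reports neutropenia in 69.2% and thrombocytopenia in 36.3% of patients on single-agent trabectedin, and describes transaminase rises as common. Section 1.5 names transaminitis as a potential overlapping toxicity of the combination. If sites differ in what they enter, grade 1-3 laboratory rates by dose level and cohort would partly reflect recording habit, and no planned output would reveal it.

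**Working it through.** There is no stated figure to reproduce. The check follows the laboratory data from collection to output.

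**1. Collection.** Under Protocol 4.7, haematology and biochemistry after the first dose fall on days 8 and 15 of cycle 1, days 1, 8 and 15 of cycle 2, and day 1 of cycle 3. That is 2 + 3 + 1 = 6 dated sets by the start of cycle 3, with at least one per cycle afterwards.

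**2. Use in the SAP.** Haematology and biochemistry variables appear in the eligibility checks of SAP 2.2.2. None appears under graded toxicity in 3.2.3. Counting the planned outputs:

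| SAP section | Outputs | Using on-treatment haematology or biochemistry |
|---|---|---|
| 4.1 | 4 listings | 0 |
| 4.2 | 10 listings | 0 |
| 4.3 | 32 tables, 2 figures | 0 |

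The blood biomarker and circulating-DNA entry in 3.2.4 is pharmacodynamic and does not fill this gap.

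**3. Route from value to AE record.**
- Grade 4: an explicit rule in 10.2.2, independent of clinical relevance.
- Grades 1 to 3: abnormal findings are AEs by definition (10.2.1), and non-serious AEs are entered in the CRF by the investigator (10.8). No text says which values must be entered, when, or that grades are derived from the values.
- 11.2.1 concerns comments on out-of-range data. It does not mention AE recording, and 10.2.1 does not mention 11.2.1.

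**4. Size.** If *c* is the share of grade 1-3 laboratory events entered on the AE form, then reported rate = true rate x *c*. The documents give no value for *c*. The rates in 1.3.3 are for trabectedin alone, pooled over three schedules, and the grade 3 and grade 4 neutropenia percentages given there belong to the 24-hour infusion, which the text describes as having higher incidence and severity. This trial uses a 3-hour infusion. Any percentage loss would rest on an assumed *c* applied to a rate from another regimen, so none is given.

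**5. What the values can say about the DLT duration criterion.** One DLT criterion is grade 3 haematologic toxicity lasting more than 7 days. Days 8 and 15 are 15 - 8 = 7 days apart. Section 4.7 allows a 72-hour window. If that means 3 days either side of each date (an assumption), the interval runs from 7 - 6 = 1 to 7 + 6 = 13 days. Two successive grade 3 values at the nominal spacing cannot alone establish more than 7 days, and the count between them is unobserved. The values can flag a case for review; they cannot settle it.

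**The case against.** The strongest reply is that 11.2.1 is not a filter. It governs comments, while 10.2.1 makes abnormal findings AEs unconditionally, so the two can be read together without conflict. This stands. A reader might infer from 11.2.1 that values judged insignificant are left off the AE form and that toxicity rates are biased downward. The documents do not say so, and they describe no difference between sites. What remains is that the reconciliation is left to the reader.

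Second, half of the primary endpoint does not depend on the AE form. DLTs have their own form with haematology items, and a laboratory abnormality can be a DLT without being an AE. The steering committee is consulted before each escalation and the IDMC reviews the MTD. This also stands. A reader might go on to infer that a missed prolonged grade 3 cytopenia could turn 2/6 into 1/6 and shift the MTD. That would require a listed DLT criterion to be missed on a dedicated form and through those reviews, and nothing in the plan points to that.

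Third, Protocol 11.2.2 provides for comparing the eCRF with original clinical or laboratory data and for checking AEs at the 100% level. SAP 4.1.3 lists dated grade changes, and SAP Table 4.3 tabulates dose reductions and delays with reasons. These reduce the risk. However, the only stated check that events have been reported at all is for serious AEs, and none of these measures yields a rate derived from measured values.

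**Conclusion.** The point holds as a gap in the planned analysis. Protocol 7.3 names laboratory changes as part of the safety evaluation, the values are collected, and 0 of 14 listings, 32 tables and 2 figures use them on treatment. Graded toxicity therefore depends entirely on AE-form entry, and for grades 1 to 3 the entry rule is left implicit between 10.2.1 and 11.2.1.

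Under-counting of asymptomatic grade 1-3 cytopenias and liver changes is possible; the documents do not show that it happens or how large it would be. No effect on the MTD is shown, and no sample size or decision rule changes. This rests on the SAP's list of outputs being complete. If a laboratory table is planned elsewhere, only the wording of 11.2.1 needs attention.

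**What to change.** **SAP 3.2.3 and 4.3.11.** Add a table of the worst CTCAE grade per patient, using the version in Protocol 8.1 (v4.03), derived from recorded haematology and biochemistry values with each laboratory's normal limits. Present it by dose level, cycle and tumour cohort beside the AE-form table.

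**Reconciliation.** List every discrepancy between the derived grades and the AE and DLT forms. Use the dated values to flag possible prolonged grade 3 haematologic toxicity for steering committee review, stating that the sampling interval does not allow them to prove the duration alone.

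**Protocol 11.2.1.** State that clinical significance governs the comment only, not AE recording or grading.

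**Cost.** Some programming and a table of normal limits for the laboratories serving the three centres. The scheduled values already exist, so no extra sampling is needed. Reported laboratory toxicity rates may rise, and the report should explain that the derived table and the AE-form table come from different sources.

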11.2.2. Monitoring

In order to guarantee the authenticity and credibility of the data in accordance with the principles of GCP (Good Clinical Practice) dated 24 November 2006, the sponsor shall implement a quality assurance system comprising:

- the management and monitoring of the trial in accordance with the procedures stipulated by the Institut Bergonié,
- the quality control of the research site data by the CRA whose role is to:
 - check compliance with the protocol, GCP and current legislation and regulations,
 - check the consent and eligibility of each patient taking part in the trial,
 - check the consistency and coherence of case report form data against the source documents.
 - check that each serious adverse event is reported,
 - monitor the traceability of the study medication (dispensation, storage and drug accountability),
 - check, where applicable, that the persons likely to take part in the trial are not already participating in another trial that could prevent them from being included in the clinical trial proposed. The CRA shall also ensure that the patients have not participated in a trial for which an exclusion period currently applies.

- The possible audit and inspection of study centers
- The centralized review of certain protocol criteria.

The check procedures will include:

- Study progression,
- Protocol compliance,
- The updating of information on the Internet site.

The checking of data by comparing the information on the electronic case report form and the original clinical or laboratory data is one of the monitoring procedures.

The following will be checked, in particular, for each patient (100% level): patient identification, informed consent (procedure and signature), selection criteria, therapeutic procedure, adverse events, principal response variables. The personal data relating to each patient shall remain confidential. On the electronic case report form or any other form dispatched, the patients will be identified solely by their initials (1 /name – 1 /surname) and an inclusion number. However, the investigators must keep a list identifying the patients in their folders.

The CRAs responsible for the quality control of this clinical trial are duly appointed by the sponsor for this particular purpose and must have access, with the consent of those involved, to individual trial participant data required strictly in accordance with this control procedure. The CRAs are subject to professional secrecy under the conditions defined by Articles 226-13 and 226-14 of the French penal code. The traceability of monitoring visits is guaranteed by a written monitoring report.

The investigators shall undertake to give CRAs direct access to the medical records of each patient in order to allow the CRAs to ensure optimal quality control of the trial. The same applies to health authority representatives.

11.2.3. Handling of missing data

The monitoring of data for adverse events will be carried out regularly in order to effectively limit the amount of missing data likely to prevent or hamper trial implementation and analysis.

11.2.4. Audits/Inspections

The sponsor, the local authorities or the authorities to which information about this study has been submitted can decide to have an audit. All the documents relating to this study must be available for such an inspection after prior notification.

11.2.5. Data management

The data are entered using an electronic case report form (e-CRF) created with Macro 4.2 (Infermed limited 2010). Data entry is performed by the CRA-I using login and password provided by the database administrator. It is carried out at the research unit of Bergonie Institute.

Each step of the data management is described in the data management plan (DMP) drafted by the data manager. This document is validated by the coordinating investigator, the statistician, the CRA-C and the database administrator and is performed according to the internal procedures of the research unit.

The process of data lock/unlock is performed according to our procedure and after validating a check list.

All data will be backed-up daily and kept for 30 days.

12. REGULATORY ASPECTS AND ETHICAL CONSIDERATIONS

Clinical Research Management Unit – Institut Bergonié Contacts:

[name] – [contact], e-mail: [contact]
or [name] – [contact], e-mail: [contact]

The study will be carried out in accordance with:

- Law no. 2012-300 dated 5 March 2012 (law "Jardé") relating to researchs involving the human person.
- The ethical principles of the current version of the "Declaration of Helsinki" ([available on its full version on the site <http://www.wma.net>](http://www.wma.net)).(Appendix 4)
- Good Clinical Practice (GCP): I.C.H. version 4 of 9 November 2016 and decision dated 24 November 2006 (Official Bulletin of 30 November 2006).
- European Directive (2001/20/EC) on clinical trial procedures.
- Huriet's law (No. 88-1138) dated 20 December 1988, concerning the protection of persons taking part in Biomedical Research with the provisions of the Public Health law (No. 2004-806) of 9 August 2004 and implementing decree No. 2006-477 of 26 April 2006 relating to biomedical research.
- The French law on Data Protection and Civil Liberties, No. 78-17 of 6 January 1978 amended by law No. 2004-801, dated 6 August 2004, concerning the protection of persons with regards to the processing of personal data.
- The French law on Data Protection and Civil Liberties, No. 78-17 of 6 January 1978 amended by law No. 2004-801, dated 6 August 2004, concerning the protection of persons with regards to the processing of personal data.
- The application of Circular DHOS/INCA/MOPRC/2006/475 of 7 November 2006: the Sponsor shall undertake to register the Trial and thus make it accessible to the general public, in the INCa (French Cancer Institute) register via the Internet site: www.e-cancer.fr. Each trial published in the INCa register will be sent to the NCI for registering on the following site: www.clinicaltrials.gov. The trial will be registered before the first patient is entered into the study. The Sponsor is responsible for updating the study data in order to guarantee the reliability of the information available on-line.
- Law no. 2004-800 dated 6 August 2004, concerning bioethics, amended by law No. 2012-387, dated 22 March 2012.

12.1. Clinical Trial authorization

This trial is registered under EudraCT N° 2016-004720-33.

The protocol has been approved by the South West and Overseas Territories III Ethics Committee, Bordeaux. Approval was given on |_2_|_1_|/|_1_|_2_|/|_2_|_0_|_1_|_6_|.

The Relevant Authority, the Agence Nationale de Sécurité du Médicament et des Produits de Santé (ANSM - French Agency for the Safety of Health Care Products) authorized the clinical trial on |_0_|_5_|/|_0_|_5_|/|_2_|_0_|_1_|_7_|.

Any amendments to the protocol concerning study objectives, patient population and principal methods will require an amendment, which must be approved by the EC and l'ANSM. The sponsor will inform the EC and ANSM of expected and/or unexpected serious adverse events in accordance with current regulations and within 30 days after of completion of the trial.

The sponsor will send the summary of the final report to the relevant Authority within one year of completion of the trial.

The sponsor has made a commitment to compliance the Reference methodology for the processing of personal data carried out in biomedical research: Référence methodology MR-001. This commitment of compliance is registered under No 118019 of the 07/11/2006.

